Study Protocol, Including Statistical Analysis Plan

Study Title: The Effect of Reducing Posttraumatic Stress Disorder Symptoms on Cardiovascular Risk

NCT Number: NCT02736929

Document Date: 1/12/2021

Full Protocol: The Effect of Reducing Posttraumatic Stress Disorder Symptoms on Cardiovascular Risk Principal Investigators: [name]. and [name].

A. SIGNIFICANCE AND SPECIFIC AIMS

Coronary heart disease (CHD) remains the leading cause of morbidity and mortality in the U.S., and it is now known that CHD prevalence can be explained by both traditional risk factors and psychosocial risk factors (Lichtman, Bigger, Blumenthal et al., 2008; Wielgosz & Nolan, 2000). An increasing body of evidence suggests that posttraumatic stress disorder (PTSD) may be causally related to accelerated CHD development and may also be a trigger of fatal cardiac events in civilians and in veterans (Boscarino, 2008; Vaccarino et al., 2013). Our understanding of the association between PTSD and CHD risk comes from several recent studies, including several 13-14 year follow-up studies in which PTSD is associated with a 2- to 3-fold increased risk of CHD (Boscarino, 2008; Vaccarino et al., 2013; Kubzanksy, Koenen, Jones, & Eaton, 2009). However, PTSD is also associated with psychiatric comorbidity and with cardiovascular risk behaviors such as smoking, substance abuse, obesity, and poor medical adherence, which may contribute to the observed association between PTSD and CHD risk. Although some studies are thought to indicate the presence of a direct and independent association between PTSD and CHD, they remain confounded by the potential contribution of adverse health behaviors, as well as by the stability of PTSD symptoms during the period over which CHD outcomes were monitored (Boscarino, 2008; Vaccarino et al., 2013). As stated in a recent editorial, an important next step before PTSD can be recognized as an independent CHD risk factor is to address the limitations of our understanding of the mechanisms by which PTSD symptoms convey CHD risk burden, including the need to determine how changes in PTSD symptoms affect CHD risk (Sidney, 2013).

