The study will also determine whether successful treatment of PTSD symptoms improves the cardiac biomarkers proposed to underlie the excess CHD risk in PTSD.

Overview of the Study Approach. The proposed randomized controlled trial (RCT) uses an evidence-based intervention, CPT-C ([name] & Schnicke, 1992), as a tool to induce greater change in PTSD symptom severity compared to WP-CON. The use of a RCT design strengthens our results by controlling and quantifying variability and reducing potential confounding due to selection bias and will enable us to carry out our main goal which is to examine whether changes in PTSD symptom severity impact changes in CHD risk biomarkers. One hundred and twenty men

Figure 1. Pathophysiological Pathway to CHD in PTSD

and women (40-65 years of age) with current PTSD will be randomly assigned in a 2:1 ratio to receive CPT-C or to participate in a waiting period control (WP-CON) condition with minimal attention; CHD biomarkers will be evaluated at baseline and again after completion of CPT-C or after the WP-CON period (see Figure 2). Randomization will be stratified by variables known to be related to both PTSD and to CHD outcomes (gender, age [dichotomization point: 50 years], and comorbid Major Depressive disorder). During the treatment or waitlist phase of the study, PTSD symptoms will be measured every two weeks in each study arm in order to assess changes therein. The WP-CON group will receive minimal attention in the form of weekly telephone calls to assess current emotional state and to provide supportive, nondirective, brief counseling if participants report experiencing a crisis. All prerandomization baseline and post-intervention assessments of PTSD symptoms, psychosocial measures, health behaviors, and CHD biomarkers will be performed by assessors who are blinded to participants' randomization condition.

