General Analytic Strategies. We will examine all variables to determine if parametric distributional assumptions are valid (e.g., normality for the continuous variables). Variables not meeting approximate distributional assumptions will either be transformed or modeled using nonparametric methods. In addition, we will explore the variability and correlation structure of the CHD outcome variables and PTSD symptom severity. Evidence of imbalance in baseline demographic (age, gender, veteran/civilian status) or clinical (high blood pressure, diabetes, major depression) characteristics will be noted and discussed as to whether they are clinically significant and we will consider sensitivity analyses including these covariates in models (models described below separately for each aim), as recommended by the Committee for Proprietary Medicinal Products guidelines (Committee for Proprietary Medicinal Products, 2004). We will also minimize the imbalance on variables known to be related to the predictor and outcome variables by stratifying randomization by gender, age, and major depressive disorder. As the main goal of the aims for this study is to understand how changes in PTSD symptom severity impact changes in CHD markers, we will conduct both an intent-to-treat analysis where participants will be analyzed as part of the group to which they are randomized, regardless of intervention adherence, and a per-protocol or as-treated analysis to strengthen the evidence that the mechanism for the effects of CPT-C vs. control on CHD markers is through PTSD symptom severity changes.

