stratification variables of gender, age, and comorbid major depressive disorder (Committee for Proprietary Medicinal Products, 2004) and as identified in the detailed description of methodologies and in the general analytic section, sensitivity analysis will also include the potential important covariates of functional comorbidity, smoking status, substance abuse, and habitual physical activity. Our main analysis technique for the primary outcome, general linear models via maximum likelihood estimation, uses all available data on subjects, rather than using only subjects with completely observed information, implicitly accommodating missingess when related to prior outcome, or to other baseline covariates included in the model (defined as missing at random).

Aim 2: To examine mechanisms of change in CHD risk biomarker outcomes in a mediation framework. It has been repeatedly demonstrated that individuals suffering from PTSD show excessive SNS, reduced PNS activity, chronic inflammation, and endothelial dysfunction and a number of studies have presented evidence suggestive of the possibility that these CHD markers of risk may be normalized following PTSD treatment (Cohen et al., 2000; Nishith et al., 2003; Blanchard et al.2002; Rabe et al., 2006; Hinton, Hofmann, Pollack, & Otto, 2009). The objective of this aim is to examine whether the change in PTSD symptoms explains the change in CHD biomarkers observed following CPT-C. To achieve this objective, we will test the working hypothesis that improvements in CHD risk biomarkers will be mediated by reductions in PTSD symptom severity. These findings will help establish whether PTSD symptoms themselves are determinants of CHD risk, independently of psychiatric comorbidity and health behaviors associated with cardiovascular risk. When the proposed studies for aim #2 have been completed, it is our expectation that the magnitude of the contribution of PTSD symptom load towards each of the evaluated CHD risk biomarkers will be clarified. Such a finding would be of importance, because it would provide support for a direct role of PTSD symptoms in the CHD risk observed in PTSD and would also identify which cardiac biomarker would provide the most utility in screening and CHD risk stratification in order to predict and prevent the onset of CHD.

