treatment group: $C = \gamma_0 + \gamma_1^*$ treatment. We then fit a model examining the relationship between the mediator and post-treatment change in CHD biomarkers (Y): Y = β_0 + treatment* β_1 + C* β_2 . Finally, to show mediation, we will test that the product of γ_1 and β_2 is not equal to 0 using an extension of the Sobel first-order test (Fritz & MacKinnon, 2007); that is, the the effects of CPT-C on CHD risk biomarkers are attributable to its effects on PTSD symptom improvement. To fully understand these relationships, we will also investigate the MacArthur approach, where our second model will be (Y): Y = β_0 + treatment* β_1 + C* β_2 + C* treatment * β_3 . Under this approach, improvements in CHD biomarkers are attributable to improvements in PTSD symptoms if there is evidence that γ_1 is not equal to 0, and either β_2 or β_3 are not equal to zero. The model will also be adjusted for stratification variables of gender, age, and major depressive disorder, and as detailed above in the general analytic section in the sensitivity analysis, we will evaluate and include other potentially important covariates, including change in anxiety and depressive symptoms estimated from the changes in HADS anxiety and depression following the intervention. We will also explore an as-treated analysis to maximize the potential mediation effects of PTSD symptom severity changes over time. For these analyses, data will be deemed usable for any individual who drops out of the study after two weeks or more of CPT-C or WP-CON, if PTSD symptom change is available and a repeat CHD biomarker assessment can be performed after the PTSD symptom change is assessed.

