
Medications, Health Risk Behaviors, and Psychosocial Assessments. During the screening period, we will collect demographic, health risk, and other clinical and demographic information, including age, gender, race, weight, height, central adiposity (waist-hip ratio), and current medication use. We will ask participants to describe any counseling treatment for PTSD that they may be receiving. We will also check for the presence of cognitive impairment using the Montreal Cognitive Assessment (MoCA; Nasreddine et al., 2005). This tool has been used as a short cognitive screening tool for identifying impaired cognitive functioning in the general population; scores range from 0 to 30, and any individual

who scores below 20 will be excluded from participation due to the presence of cognitive impairment (Gallagher et al., 2013). Although the cut score of 26 has good specificity and sensitivity to diagnose mild cognitive impairment (MCI; Hoops et al., 2009), we do not wish to rule out participants with MCI, but rather those with dementia. A cut score of 26 will likely otherwise suitable participants, as CPT has been successfully used in patients with traumatic brain injury (TBI) and MCI. Any participant who is excluded due to low MoCA scores will be informed of the results and encouraged to discuss the findings with their personal physician or care provider for further evaluation and treatment if necessary. In addition, to account for the impact of comorbid somatic disease on the CHD biomarkers, we will measure use a modified version of the Functional Comorbidity Index (Groll, Bombardier, & Wright, 2005), which provides a dimensional score based on the summation of the self-reported diagnoses of arthritis, osteoporosis, asthma, COPD, diabetes, gastrointestinal disease, and degenerative disk disease, which are treated as binary variables. In women, we will also determine menopausal status, and will use the classification system proposed by Tom and colleagues (Tom, Kuh, Guralnik, & Mishra, 2010). Prior to participants wearing the Holter monitor, we will ask them to indicate their smoking and alcohol use on the Coping Behaviors scale, as these factors could affect heart rate variability and catecholamine excretion. Participants will be asked about new onset of infections and exacerbations of any current chronic diseases that might affect inflammation (Medical Disease Change Form).

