0.50	40	0.55	22.0
0.50	50	0.55	27.5
0.60	40	0.50	20.0
0.60	50	0.50	25.0

assumed a range of correlations between 0.3 and 0.6 and standard deviations (SD) of 40 and 50. **Table 2** presents effect size differences with 120 subjects. Using the most conservative assumptions, with 80% power, alpha=0.05, SD=50, rho=0.3, and 20% attrition rate by 7-weeks we can detect an effect size difference of 0.60 (Cohen, 1988), corresponding to a difference of 30 units in mean HRV levels at 7-weeks between CPT-C and control. For the AIM 2 mediation analysis, we will test that the effect of CPT-

C on CHD biomarkers is attributable to changes in PTSD severity. We determined detectable effect sizes for mediation based on empirical power estimates for the product-of-coefficient test (i.e., the product of γ_1 and β_2) given by Fritz and MacKinnon (2007). With 120 subjects and a type-I error of 0.05, we will have 80% power to detect medium to large effect size differences for each of the parameters individually (e.g, γ_1 and β_2) that are part of the product test.

Missing Data. Our plans for preventing and dealing with missing data follow the guidelines set forth by the National Research Council's Panel on Handling Missing Data in Clinical Trials. First, , we have numerous strategies in place to prevent attrition; based on prior experience with a similar design and population, we anticipate that we will have less than 20% attrition. Second, as recommended by the panel, we will conduct two general types of sensitivity analyses for our primary analysis. If the missing values are related to measured factors, such as treatment group or baseline comorbidities, then multiple imputation will be used to incorporate information for these auxiliary variables while still preserving a parsimonious main treatment effect model (Collins, Schafer, & Kam, 2001). As a first sensitivity analysis, we will construct a general, multivariate imputation model using all observed CHD markers, treatment group, and any covariates predictive of missingness (Olsen, Stechuchak, Edinger, Ulmer, & Woolson, 2012). The primary analysis models will then be fit to the multiply imputed data and the estimates and standard errors will be combined using appropriate combining rules. We acknowledge the possibility that data may be missing not at random and propose as a second sensitivity analysis to explore pattern-mixture models and the toolkit of methods recently advocated by O'Kelly and Ratitch (2014).

References

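### The main Aim 2 mediation model adjusts only for gender, age and major depression, leaving the non-randomized symptom-to-biomarker path open to confounders the protocol itself names

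*Combined protocol and SAP*

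**What the plan says.** **Mediation models (Aim 2, Analytic strategy).** Symptom change C is regressed on treatment (coefficient γ1). Biomarker change Y is then regressed on treatment and C (coefficient β2 for C). Mediation is shown if γ1×β2 differs from zero by an extension of the first-order Sobel test. A second, MacArthur version adds a C-by-treatment term β3 and attributes the benefit to symptoms if γ1 is non-zero and β2 or β3 is non-zero. The main model adjusts for the three stratification variables: gender, age and major depressive disorder. For sensitivity, "as detailed above in the general analytic section in the sensitivity analysis, we will evaluate and include other potentially important covariates"; the only ones named are changes in HADS anxiety and depression.

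**The section it points back to (General Analytic Strategies).** "Evidence of imbalance in baseline demographic (age, gender, veteran/civilian status) or clinical (high blood pressure, diabetes, major depression) characteristics will be noted", and "we will consider sensitivity analyses including these covariates in models (models described below separately for each aim".

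**Where the health variables appear.** Section A says of earlier PTSD–CHD studies that "they remain confounded by the potential contribution of adverse health behaviors", and lists smoking, substance abuse and obesity among the risk behaviors that go with PTSD. The Aim 1 sensitivity analysis names "functional comorbidity, smoking status, substance abuse, and habitual physical activity". The Measures section collects "weight, height, central adiposity (waist-hip ratio), and current medication use", but adiposity is in no covariate list. It also offers smoking, alcohol abuse and sedentary behavior as possible moderators.

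**The intended inference.** The Aim 2 rationale expects to establish whether symptoms determine CHD risk independently of psychiatric comorbidity and health behaviors.

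**The concern.** The Overview of the Study Approach credits the randomized design with "reducing potential confounding due to selection bias and will enable us to carry out our main goal", that goal being whether symptom change affects biomarker change. Randomization does this for treatment contrasts: the Aim 1 comparison and γ1. It does not do it for β2. Within an arm, nobody is randomized to improve more or less, and a baseline characteristic that predicts both symptom improvement and biomarker change will produce a non-zero β2 even if symptoms have no effect on the biomarker.

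Balance between arms offers no reassurance, because a factor distributed identically in both arms can still confound β2. The HADS changes are no substitute: they arise after randomization, may themselves respond to therapy, and do not stand in for baseline smoking, drinking, activity, weight or somatic disease.

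At stake is the trial's mechanistic conclusion. Under the main model a confounded γ1×β2 would be reported as benefit attributable to PTSD improvement, which is the ambiguity Section A finds in the earlier literature.

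**Working it through.** **1. Sample size in play.** Power Analysis gives 120 randomized 2:1 (80 and 40), "with 80% power, alpha=0.05, SD=50, rho=0.3, and 20% attrition rate by 7-weeks". Completers: 0.8×80 = 64 and 0.8×40 = 32, total 96. As a check, the detectable effect is (1.96 + 0.84)×√(1/64 + 1/32)×√(1 − rho²), with √(1/64 + 1/32) = 0.2165. For rho 0.3, 0.4, 0.5 and 0.6 this gives 0.579, 0.556, 0.525 and 0.485. Rounded to the nearest 0.05 these are 0.60, 0.55, 0.55 and 0.50, matching Table 2, so 96 is the plan's own analysis size.

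**2. Assumptions not in the documents.** Treatment shifts C by 0.8 SD. One composite confounder U is independent of arm and has within-arm correlation a with C and b with Y. True β2 and the direct treatment effect are both zero. The documents give no values for a or b, so a range is shown.

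**3. Bias by hand.** With unit within-arm variances, omitting U gives β2 an expected value of a×b, with standard error about √((1 − (ab)²)/93). Power for γ1 is that of z = 0.8/0.2165 = 3.70, about 0.959. For a = 0.3, b = 0.4: bias 0.12, SE 0.103, ratio 1.17. The chance that β2 is significant is about 0.214, and the chance that both paths are is 0.214×0.959 = 0.206.

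**4. Simulation of the two Aim 2 equations** (at least 6,000 trials per setting). The product test uses z = γ1β2/√(γ1²·SE(β2)² + β2²·SE(γ1)²).

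| a / b | Bias in β2 | Both paths significant, by hand | Both paths significant, simulated | Sobel, U omitted | Sobel, U included |
|---|---|---|---|---|---|
| 0 / 0 | 0 | 5% | 5% | 2% | 2% |
| 0.2 / 0.2 | 0.04 | 6% | 6–7% | 3–4% | 2% |
| 0.25 / 0.30 | 0.075 | 11% | 11% | 5% | 2% |
| 0.3 / 0.4 | 0.12 | 21% | 20% | 12% | 2% |
| 0.4 / 0.4 | 0.16 | 33% | 32% | 20% | 2–3% |

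The simulated rate with both paths significant returns to about 5% when U is included. That rule is the closer guide to the MacArthur criterion, which lacks the Sobel test's conservatism.

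**5. Does balance help?** Forcing U to be exactly balanced between arms and omitting it gives Sobel rates of 3.2%, 7.0% and 20.4% at a = b = 0.2, 0.3 and 0.4. With U independent of arm but not forced to balance, they are 3.1%, 7.6% and 20.5%. Balance makes no material difference.

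**6. Does better retention help?** No. With all 120 analyzed, the rates at a = b = 0.3 and 0.4 are 9.8% and 30.0%, because the bias stays fixed while the standard error shrinks.

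**7. Residual correlation that matters.** At n = 96, a within-arm correlation of 0.20 gives t = 0.20×√93/√(1 − 0.04) = 1.97, against a critical value of 1.99. A spurious correlation just over 0.20 is enough to make β2 significant.

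**The case against.** Four points on the other side carry weight.

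- **Stable behaviors may cancel.** C and Y are both change scores, so a behavior that shifts only their levels drops out, and Aim 1's Expected Results anticipates little or no behavior change during the study. This stands as a limit on size. It does not remove the problem, since baseline smoking, drinking or weight can still predict how much a person changes.
- **The correlations are assumed.** This stands. At 0.2/0.2 the Sobel rate stays below nominal, and at 0.25/0.30 it is about nominal (though above the roughly 2% obtained with adjustment).
- **Aim 2's sensitivity wording is open.** It resembles the Aim 1 sentence listing comorbidity, smoking, substance abuse and activity, and a fair reader may carry that list across. Even so, those variables would not enter the model that decides mediation, and adiposity would still be missing.
- **Some confounding is addressed.** Major depression is in the main model. The Functional Comorbidity Index is collected to account for somatic disease, and HADS changes are tested as competing mediators.

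A reader might also infer that covariates for every aim are chosen by arm imbalance, or that General Analytic Strategies is what keeps the health behaviors out of Aim 2. The documents support neither. The main models for Aims 1 and 2 use stratification variables fixed in advance, Aim 1's sensitivity covariates are named outright, and Aim 3 adds baseline demographic and clinical covariates with no imbalance condition. The imbalance text governs only sensitivity analyses, sets no p-value trigger and does not list these behaviors. The omission comes from Aim 2's own choice of covariates; the general section merely fails to repair it.

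**Conclusion.** The point holds as a specific weakness of the Aim 2 main model and as an inexpensive improvement. β2 is not protected by randomization, and factors the protocol itself recognizes are left out of the deciding model, so that model cannot support the intended claim of independence from health behaviors.

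The size is conditional. With 96 completers, a 0.8 SD treatment effect on symptoms and no true mediation, the excess of false claims is negligible when the confounder correlates about 0.2 with both changes and serious at about 0.3–0.4. Rates are higher if the MacArthur criterion is used to claim mediation. Nothing in the documents shows which case applies, so it would be wrong to conclude that a mediated effect found here is false. The supportable statement is that the main model could not tell a real effect from one produced by these factors. The Aim 1 treatment comparison is unaffected.

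**What to change.** In the Aim 2 analytic strategy, add a fixed set of baseline covariates to both the mediator and the outcome equation, including the MacArthur version, regardless of balance between arms: smoking status, AUDIT-C, Stanford 7-day activity, BMI or waist-hip ratio (choose one in advance), and the Functional Comorbidity Index, alongside gender, age and major depressive disorder. Keep HADS changes as a separate sensitivity analysis. State that arm imbalance is not a criterion for choosing Aim 2 covariates.

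Add one sensitivity analysis reporting the residual mediator–outcome correlation at which the indirect effect would no longer exclude zero. The value of about 0.20 in the working gives readers a benchmark.

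The cost is SAP wording and modest analysis, with no new data: about five degrees of freedom out of about 96. If the covariates explain 10–20% of symptom change, the standard error of β2 rises by a factor of 1/√0.90 = 1.05 to 1/√0.80 = 1.12, offset to the extent that they also explain biomarker change. Aim 3 already adds baseline covariates and does not need this change.

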Expected Results. Because there are limited data and no studies evaluating the short-term effects of CPT-C on CHD biomarkers, HRV was selected as the primary outcome based on our limited pilot data; the other CHD markers will be secondary outcomes. We hypothesize that all CHD biomarkers will show improvement following CPT-C when compared to WP-CON, and the changes will be independent of changes in cardiovascular health risk behaviors, as defined by smoking, alcohol use, and low physical activity measured using the Stanford 7-day physical recall survey (Blair et al., 1985). It is likely that these cardiovascular health behaviors will remain constant or minimally change over the time period of the study.

Analytic strategy. The primary CHD risk biomarker, HRV, and secondary CHD risk biomarkers are continuous measures collected at baseline and 7-weeks (post-treatment) and therefore the same modeling strategy will be used for all CHD biomarker outcomes. To test the primary hypothesis of a CPT-C effect at post-treatment, we will use a general linear model that accounts for the correlation between participants' repeated outcome measurements over time with an unstructured covariance matrix (Verbeke & Molenberghs, 2000; Fitzmaurice, Laird, & Ware, 2004). The general form of the model is $Y_{it} = X_{it}\beta + \epsilon_{it}$, where Y_{it} is the CHD marker for subject i at time t=0 and 7 weeks. The predictors (X_{it}) in the model will include time and the CPT-C arm by time interaction. We will estimate the model parameters using the SAS procedure MIXED (SAS Version 9, Cary, NC), and contrasts will be written in the context of this model to test the difference of mean change in CHD markers between the two treatment arms at week 7. For improvement in precision, the model will also be adjusted for

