Approach. This RCT with repeated measurements of PTSD symptoms and CHD markers will provide a mechanism to evaluate the temporal relationship between the change in PTSD symptoms and the changes in ANS control mechanisms, endothelial function and inflammation. Using this temporal relationship, we will examine whether changes in PTSD symptoms mediate the effects of CPT-C on CHD markers.

Expected Results. We anticipate that the change in PTSD symptoms will mediate the relationship between CPT-C and CHD marker change, thereby identifying the role of reduction in PTSD symptoms as a mechanism for the improvement in CHD risk.

Analytic strategy. We propose to conduct mediation analyses using the more commonly known Baron and Kenny approach (Baron & Kenny, 1986) as well as the newer MacArthur approach (Kraemer, Kieser, Essex, & Kupler, 2008). By the MacArthur definition, the potential mediator must be during or post-treatment; therefore, the change in PTSD symptoms severity between week 0 and week 6 will be considered as a potential mediator. The outcome then will be participants' post-treatment change in CHD risk biomarkers, which will be determined at week 7. We will also explore the role of trajectories of change in PTSD symptom severity as a mediator of the post-treatment change in CHD risk biomarkers by deriving an individual-level summary measure of PTSD symptom change using the successive PTSD symptoms assessed at two week intervals. We will first fit a model to examine the relationship between the mediator (C) (i.e., change in PTSD symptoms during treatment) and

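### Aim 2 claims to evaluate the temporal relationship between symptom change and biomarker change, but with one post-baseline biomarker value the design orders the measurements, not the changes, and the mechanism wording is too strong

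*Combined protocol and SAP*

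**What the plan says.** All references are to the combined protocol and SAP.

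- **Temporal claim (Aim 2, Approach).** Repeated measurement of symptoms and markers "will provide a mechanism to evaluate the temporal relationship between the change in PTSD symptoms and the changes in ANS control mechanisms". The same sentence extends this to the other markers. The mediation analysis is then said to use that temporal relationship.
- **Biomarker timing (Overview of the Study Approach; Aim 1, Analytic strategy).** "CHD biomarkers will be evaluated at baseline and again after completion of CPT-C or after the WP-CON period". Aim 1 puts the second assessment at week 7 for every marker.
- **Mediator and outcome (Aim 2, Analytic strategy).** For the mediator: "the change in PTSD symptoms severity between week 0 and week 6 will be considered as a potential mediator". On the biomarker side, the change is read one week later than that: "The outcome then will be participants' post-treatment change in CHD risk biomarkers, which will be determined at week 7". A further mediator, an individual trajectory summary, is derived "using the successive PTSD symptoms assessed at two week intervals".
- **Models (Aim 2, Analytic strategy).** Symptom change C is regressed on treatment (coefficient γ1). Biomarker change Y is regressed on treatment and C (coefficients β1 and β2). Mediation is declared if a first-order product test rejects γ1β2 = 0. A second version (MacArthur) adds a C-by-treatment term.
- **Adjustment (same section).** The main model adjusts for gender, age and major depressive disorder. Sensitivity analyses add other covariates, naming change in HADS anxiety and depression.
- **Planned conclusion.** The analytic strategy says that biomarker effects are attributable to symptom improvement. Expected Results anticipates mediation, "thereby identifying the role of reduction in PTSD symptoms as a mechanism for the improvement in CHD risk".

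**The concern.** To say that symptom change preceded biomarker change, one needs to know how far the biomarker had moved at some point during treatment. The plan takes no such measurement. Only symptoms are followed every two weeks, so only the mediator has a time course.

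Randomization protects the effect of treatment on symptoms and the effect of treatment on the biomarker. It does not protect the path from symptoms to biomarker, because nobody is randomized to a degree of symptom change. Anything that moves both within an arm, such as sleep, medication or activity, produces a non-zero β2, and so does an effect running from biomarker to symptoms.

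The Significance section faults earlier studies for confounding by health behaviours and sets this trial the task of showing whether symptoms convey risk directly and independently. Aim 2 carries that inference. A significant product read as the plan reads it would claim more than the data can show.

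**Working it through.** **1. The plan's own figure.** Aim 2 gives no numeric path sizes, so its power statement cannot be reproduced. The Aim 1 figure can. With 20% attrition, 80/40 becomes 64/32. At rho = 0.3, 80% power and alpha 0.05 (taken as two-sided):

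d = (1.960 + 0.842) × √(1 − 0.3²) × √(1/64 + 1/32) = 0.579

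This matches Table 2's 0.60 after rounding to the nearest 0.05. The 64/32 split is used below.

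**2. Windows side by side.** The mediator is change over weeks 0-6 and the outcome is change over weeks 0-7. They share six of seven weeks, with no biomarker value between baseline and week 7.

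**3. Two directions, one data set.** Suppose symptoms truly drive the biomarker: C = 0.8T + e and Y = 0.5C + e′, with unit error variances. These path sizes are assumptions. Now reverse the direction, with no effect of C on Y:

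- Y = (0.8 × 0.5)T + error = 0.40T + error, variance 1 + 0.5² = 1.25
- C depends on Y with slope 0.5/1.25 = 0.40 and on treatment with coefficient 0.8 − 0.40 × 0.40 = 0.64; error variance 1 − 0.25/1.25 = 0.80

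Both models give the same joint distribution of (T, C, Y). In simulation the product test rejected 97.6% (true mediation) and 97.9% (reverse) at N = 120, and 92.9% and 91.7% at N = 96. The fitted slope was 0.50 each time. No analysis of these two-point data alone can tell them apart.

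**4. Shared cause.** Let C = 1.0T + e1 and Y = τT + r·e1 + √(1 − r²)·e2. Symptoms have no effect on the biomarker, r is the within-arm (residual) correlation of the two changes, and τ is the true arm effect. The planned second model then estimates β2 = r and β1 = τ − r. The values of r and the 1 SD effect on symptoms are assumptions. There were 4,000 simulated trials per setting, with 64/32 completers.

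| Residual correlation r | Product test significant (τ = 0) | Also significant same-direction arm difference, τ = 0 | Same, τ = 0.6 SD |
|---|---|---|---|
| 0.2 | about 40% | about 1% | about 32% |
| 0.3 | about 77% | about 2% | about 63% |
| 0.4 | about 96% | about 3% | about 76% |

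At r = 0 the product test rejects about 3%. Repeat runs differ by up to about 3 points. With a smaller treatment effect on symptoms, the product-test rates at r = 0.2, 0.3 and 0.4 are 32, 67 and 90% (0.8 SD) and 20, 46 and 66% (0.6 SD).

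The 0.6 SD in the last column borrows the size in Table 2 but is expressed in residual SDs of biomarker change. At rho = 0.3 the SD of change is √(2 × 0.7) = 1.18 baseline SDs, so Table 2's 0.60 would be 0.60/1.18 = 0.51 on this scale.

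**The case against.** **The order is respected: symptoms at week 6, biomarker at week 7.** True of the measurements, and it meets the MacArthur condition that the mediator be measured during or after treatment. The as-treated rule for drop-outs likewise requires the biomarker assessment to follow the symptom assessment. But the outcome is change from week 0, so the order of the changes stays unknown. The trajectory summary refines the mediator only. Time 3 applies to the control arm only, enters no Aim 2 model and adds no value during treatment.

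**The simulated rates need a null world.** The 40-96% figures do not require any treatment effect on the biomarker. With none, Aim 1 would usually be null, and the fitted direct effect would usually have the opposite sign to the indirect effect (β1 = −r), a visible warning. This stands: with a same-direction arm difference also required, the rates fall to about 1-3%. However, the plan states no such requirement, and with a real arm effect the rates remain 32-76%. The correlations are assumptions, and since β2 estimates that correlation, the figures show how readily the test detects a correlation, not how likely confounding is.

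**The plan adjusts for more than the stratification variables.** Correct. A reader might infer that nothing else is considered, but Aim 2 names HADS change among its sensitivity covariates, Aim 1 lists functional comorbidity, smoking, substance abuse and physical activity, and the Measures section plans HADS change as a competing mediator. These cover measured factors only.

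**The causal language is hedged in places.** Expected Results is framed as anticipation and speaks of one mechanism among possible others. The attribution wording in the analytic strategy is not hedged.

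**Conclusion.** The point stands as one of inference and wording. One post-baseline biomarker value and overlapping change windows cannot establish the temporal relationship that Aim 2 claims. A significant product of coefficients supports attribution only if there is no unmeasured mediator-outcome confounding and no reverse effect. The plan neither states these assumptions nor tests sensitivity to them.

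Three stronger readings are tempting and not supported. First, 40-96% is not the probability that this trial will report a false mechanism: it is conditional on assumed correlations, a 1 SD symptom effect and a decision rule that looks at the product alone. Second, mediation is not untestable: it can be examined as an association consistent with a mechanism. Third, the randomized comparison of biomarkers in Aim 1 is not weakened.

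**What to change.** 1. Delete the claim that the design evaluates the temporal relationship between the two changes.
2. Replace the attribution and mechanism wording with: *consistent with mediation, assuming no unmeasured mediator-outcome confounding and no reverse effect*.
3. Add baseline biomarker and baseline PCL-5 to the Aim 2 models. Both are collected; neither appears in the stated equations.
4. Report the residual mediator-outcome correlation at which the indirect effect reaches zero. This addresses confounding; reverse direction has to remain a stated assumption.

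An earlier symptom window, such as weeks 0-4, is not recommended as a remedy: it largely duplicates the planned trajectory summary and cannot settle order while the biomarker change still spans weeks 0-7.

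The cost is plan wording and a standard sensitivity analysis on data already being collected, with no new visits or participants. The downside is a more cautious Aim 2 conclusion.
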